#### 5. **Specific Aims and Hypotheses:**

Our immediate, primary aim (#1): to test the effect of the intervention on stroke caregivers' depressive symptoms at approximately 11 and 19 weeks after baseline data collection. Hypothesis #1 (primary): Stroke caregivers who receive the intervention will have less depressive symptoms at approximately 11 and 19 weeks after baseline data collection compared to stroke caregivers in the usual care group.

We propose four secondary aims (#2-5):

Aim #2: to test the effect of the intervention on stroke caregivers' knowledge, perceived stress, burden, perceptions of positive aspects of caregiving, self-efficacy, health-related quality of life (HRQOL), and satisfaction with care at approximately 11 and 19 weeks after baseline data collection.

Hypotheses #2: (2a) Stroke caregivers who receive the intervention will have superior outcomes (i.e., greater knowledge, less stress, less burden, perceive more positive aspects of caregiving, greater self-efficacy, better health-related quality of life (HRQOL), and greater satisfaction with care) at approximately 11 and 19 weeks after baseline data collection than caregivers in the usual care group.

Aim #3: to test the effect of the intervention on Veterans' outcomes: Functional abilities and healthcare utilization (i.e., unintended hospital bed days of care, number of emergency room visits, number of unscheduled clinic visits) at approximately 11 and 19 weeks after baseline data collection.

Hypotheses #3: Veterans whose caregivers receive the intervention will have better functional abilities at approximately 11 and 19 weeks after baseline data collection and less healthcare utilization at 11 and 19 weeks after baseline data collection compared to Veterans whose caregivers are in the usual care group. Aim #4: to determine the budgetary impact for implementing the intervention.

Research question: What are the costs associated with the intervention and how do they compare to usual care?

Aim #5: to determine the facilitators, barriers, and best practices for implementing the intervention.

Research questions: What are the recommendations of VA leaders, policy makers, and clinicians for planning, developing, promoting, and evaluating and implementing the intervention in other sites? What are the caregivers' perceptions of the value, strengths, and weaknesses of the intervention, and what facilitators/barriers did they identify with the intervention?

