with covariates for baseline depression and time since discharge (*Baseline*), site (e.g., *Tampa*=1 if Tampa, 0 otherwise; and  $\beta_{3s}$  represent effects of sites compared to reference site Gainesville), time (*Time*=0 for 11 weeks, 1 for 19 weeks), and group (0 if active control, 1 if intervention). Of primary interest is the estimated within-site intervention effect at approximately 11 weeks after baseline data collection, controlling for baseline and stratifying by site. The initial test will be the test of  $\beta_8$ +  $\beta_9$ =0, which tests whether the Tampa site has a differential group effect compared to the other sites at approximately 11 weeks after baseline data collection. If a site difference in treatment effect is found, then results will be conditional on Tampa or Miami/Gainesville. In this case, the primary tests of interest will be the estimated within-site intervention effect at approximately 11 weeks after baseline data collection, controlling for baseline and stratifying by site. In the model above, this corresponds to the test of  $\beta_5$  =0 for other sites and  $\beta_5$  + $\beta_8$ =0 for Tampa. If no difference is found in our initial interaction test, we will assume that the Tampa site does not have a differential treatment effect and the interaction will be removed from the model. The new fixed effect portion of the model will simplify to the Reduced model:

$$E(y_{ij}) = \beta_0 + \beta_1 Baseline_i + \beta_2 Tampa_i + \Sigma_s \beta_{3s} I(Site_i = s) + \beta_4 Time_{ij} + \beta_5 Group_i + \beta_6 Group_i *Time_{ij}$$

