Of primary interest is the estimated within-site intervention effect at approximately 11 weeks after baseline data collection, controlling for baseline covariates and stratifying by site. In the model above, this is the test of  $\beta_5$  =0. In order to control for possible chance sample imbalances resulting from randomization, the model will include covariates for baseline prognostic factors (e.g., discharge from hospital, community living center, or rehabilitation facility; caregivers' relationship to Veteran; number of previous strokes among Veterans, etc.), deemed to have significant relationships with response and groupwise imbalances. Thus, analyses will be able to compare the groups on the measure of interest while controlling for these factors. As a supplemental analysis we will assess long term intervention effects at the approximately 19 week after baseline data collection time point. In the Full model above, this is the test of  $\beta_6$  =0 for other sites, and  $\beta_6$ +  $\beta_9$ =0 for Tampa. In the reduced model, this is simply the test of  $\beta_6$  =0. All tests will be performed at the  $\alpha$ =0.05 significance level. The correlation among observations from the same person will be accounted for through the inclusion of a random person effect into the mixed model analysis.

Hypotheses #2 (secondary): (2a) Stroke caregivers who receive the intervention will have superior outcomes (i.e., less burden, less stress, greater self-efficacy, perceive greater positive aspects of

caregiving, better HRQOL, and greater satisfaction with care) at approximately 11 and 19 weeks after baseline data collection than caregivers in the usual care group.

The analysis plan for Hypothesis 2 will closely follow the plan outlined above for Hypothesis 1 for each secondary outcome of interest.

Hypotheses #3 (secondary): Veterans whose caregivers receive the intervention will have better functional abilities at approximately 11 and 19 weeks after baseline data collection and less healthcare utilization at approximately 11 and 19 weeks after baseline data collection compared to Veterans whose caregivers are in the usual care group.

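### The 19-week test uses the wrong coefficient: β6 is the change in effect from week 11 to week 19, so a fully sustained benefit would usually be read as no 19-week effect

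*Combined protocol and SAP*

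**What the plan says.** Hypothesis #1, in Specific Aims and Hypotheses, is that caregivers in the treated arm "will have less depressive symptoms at approximately 11 and 19 weeks after baseline data collection compared to stroke caregivers in the usual care group". Both visits are therefore part of the primary hypothesis, and both are comparisons with usual care.

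Under Data Analysis, Hypothesis #1, the coding is "time (*Time*=0 for 11 weeks, 1 for 19 weeks), and group (0 if active control, 1 if intervention"). The reduced model contains β5·Group + β6·Group×Time. The full model adds β8·Tampa×Group + β9·Tampa×Group×Time. The 11-week effect is tested as β5 = 0, or β5 + β8 = 0 for Tampa when the full model is kept.

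For the later visit the plan states: "As a supplemental analysis we will assess long term intervention effects at the approximately 19 week after baseline data collection time point". It gives these tests:

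- **Full model.** "In the Full model above, this is the test of" β6 = 0 for the other sites and β6 + β9 = 0 for Tampa.
- **Reduced model.** "In the reduced model, this is simply the test of" β6 = 0.

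The Hypothesis 2 outcomes are to be analysed along similar lines, and the Barthel Index in exactly the same way.

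**The concern.** With a main effect of Group and a Group×Time interaction, the interaction coefficient is a difference between two group effects. It is not the group effect at either visit. The stated purpose is the effect at 19 weeks, but the stated contrast asks whether the effect moved between 11 and 19 weeks.

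The two questions can have opposite answers. If the benefit lasts, β6 is zero and the planned test would normally be reported as showing no long-term effect. If the benefit disappears, β6 is large and the planned test would often be significant, although the groups no longer differ at 19 weeks. The 19-week half of Hypothesis #1 has no valid stated test. The same gap is inherited by the other outcomes that follow this model and whose hypotheses also name 19 weeks.

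**Working it through.** **1. Group contrasts from the stated coding.** Set Group = 1 minus Group = 0 in the full model:

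| Sites | Week 11 (Time = 0) | Week 19 (Time = 1) | Week 19 minus week 11 |
|---|---|---|---|
| Other sites | β5 | β5 + β6 | β6 |
| Tampa | β5 + β8 | β5 + β6 + β8 + β9 | β6 + β9 |

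The reduced model gives the first row for every site. The plan's 19-week tests are the last column. They equal the 19-week effect only when the 11-week effect is exactly zero.

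**2. Could another coding rescue the text?** No. If Time were reversed (0 at 19 weeks), the 19-week effect would be β5, still not β6. The plan's use of β5 and β5 + β8 for week 11 agrees with the coding as printed.

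**3. The plan's own sample-size figure.** From Rationale for Study Sample Size: difference 3.5, SD 8.2, 84 per group, 5% level (taken as two-sided), 80% power.

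- SE = 8.2·√(2/84) = 1.265.
- 3.5/1.265 = 2.766, and Φ(2.766 − 1.960) = 0.79. This is close to the stated 80%.
- 84/(1 − 0.30) = 120 per group, as stated.

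**4. Rejection rates of the two tests.** Inputs are as in step 3. The documents give no within-person correlation ρ, so it is an assumption and is varied.

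- SE(β5 + β6) = 8.2·√(2/84) = 1.265.
- SE(β6) = 8.2·√(2(1 − ρ))·√(2/84).

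*Benefit of 3.5 at both visits* (β5 = −3.5, β6 = 0). The planned test rejects 5% of the time at any ρ. The test of β5 + β6 = 0 rejects 79% of the time. A simulation of 20,000 trials at ρ = 0.5 gave 4.9% and 78.7%.

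*Benefit of 3.5 at week 11, none at week 19* (β5 = −3.5, β6 = +3.5):

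| ρ | SE(β6) | 3.5/SE(β6) | Planned test rejects | Test of β5 + β6 rejects |
|---|---|---|---|---|
| 0.3 | 1.497 | 2.34 | 65% | 5% |
| 0.4 | 1.386 | 2.53 | 71% | 5% |
| 0.5 | 1.265 | 2.77 | 79% | 5% |
| 0.7 | 0.980 | 3.57 | 95% | 5% |
| 0.8 | 0.800 | 4.37 | 99% | 5% |

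*Benefit halved by week 19* (−3.5, then −1.75, so β6 = +1.75). The planned test rejects 22%, 28% and 43% of the time at ρ = 0.3, 0.5 and 0.7. The correct test rejects 28%. Here the planned estimate has the wrong sign for the effect that is actually present at 19 weeks.

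**The case against.** The case on the other side concerns weight, not algebra.

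- **The 19-week analysis is labelled supplemental.** The 11-week effect is the main interest, its tests are correctly specified, and neither the sample size nor data collection depends on β6. All of this is true, and it limits the damage to the later visit. But 19 weeks is named in the primary hypothesis, and no other stated test covers it.
- **The sign would warn a careful reader.** If a benefit disappears, β6 is positive on a scale where higher scores are worse. Taken at the plan's label, it would look like harm at 19 weeks, not benefit. This is correct. A false claim of benefit would require ignoring the sign, but a false claim of harm would be just as wrong.
- **A sustained benefit is missed in about 95% of trials, not always.** This also stands. The planned test still rejects at its 5% level, and estimates at each visit might be reported as well, though the plan does not say so.
- **The rates are illustrative.** They rest on an assumed correlation, full data from 84 per group at both visits, and an unadjusted comparison under the reduced model. The plan adjusts for baseline and site and does not say whether 8.2 is a raw or a residual SD. If it is raw, adjustment would raise the power of β5 + β6, while β6 would still reject at 5% under a sustained effect.
- **The carry-over is not uniform.** The wording for Hypothesis 2 is looser than for the Barthel Index, and the utilization counts use other models. The counts are not part of this point.

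**Conclusion.** The concern holds and must be fixed. Under the plan's own coding, the stated 19-week tests do not test the 19-week effect, and that conclusion needs no numerical assumption. With SD 8.2 and 84 per group, a 3.5-point benefit lasting to 19 weeks would be detected 5% of the time instead of about 79%. A benefit lost by 19 weeks would give a significant result 71% to 99% of the time for ρ between 0.4 and 0.8 (65% at ρ = 0.3), against 5% for the correct test. The primary 11-week result is unaffected.

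**What to change.** In Data Analysis, Hypothesis #1, replace the 19-week tests as follows:

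- **Reduced model:** β5 + β6 = 0.
- **Full model, other sites:** β5 + β6 = 0.
- **Full model, Tampa:** β5 + β6 + β8 + β9 = 0.

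If a test of β6 (Tampa: β6 + β9) is still wanted, keep it separately and label it as a test of whether the effect changes between visits. State that the same contrasts apply to the Hypothesis 2 outcomes and the Barthel Index.

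The same edit should correct a related slip. The initial Tampa interaction test, β8 + β9 = 0, is described as the 11-week site difference. Under this coding it is the 19-week difference, and the 11-week one is β8.

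The cost is SAP wording only, with no new data. Make the change before any unblinded analysis so that it cannot appear to be driven by the results.

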Our immediate, primary aim (#1) is to test the effect of the intervention on stroke caregivers' depressive symptoms at approximately 11 and 19 weeks after baseline data collection. Primary Hypothesis: Stroke caregivers who receive the intervention will have less depressive symptoms compared to stroke caregivers in usual care. We propose four secondary aims. Aim #2 is to test the effect of the intervention on stroke caregivers' knowledge, perceived stress, burden, perceptions of positive aspects of caregiving, self-efficacy, health-related quality of life (HRQOL), and satisfaction with care at approximately 11 and 19 weeks after baseline data collection. Aim #3 is to test the effect of the intervention on Veterans' outcomes: functional abilities and healthcare utilization (i.e., unintended hospital bed days of care, number of emergency room visits, number of unscheduled clinic visits) at approximately 11 and 19 weeks after baseline data collection. Aim #4 is to determine the budgetary impact for implementing the intervention. Aim #5 is to determine the facilitators, barriers, and best practices for implementing the intervention.

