## **Data Analysis:**

Hypothesis #1 (primary): Stroke caregivers who receive the intervention will have less depressive symptoms at approximately 11 and 19 weeks compared to stroke caregivers in the usual care group. Our primary endpoint is the caregiver depressive score. The focus of the primary analysis will be to examine the effect of the intervention based on "intention to treat." Data from all the participants will be part of the primary analyses regardless of actual number of completed in-home sessions. Thus, we are examining the effectiveness of the intervention taking into account real world compliance factors. As an exploratory study element, we will assess compliance and attempt to determine its effect on study results.

For the primary analysis, the general linear mixed model for repeated measures will be used to model the follow-up depression times (approximately 11 and 19 weeks after baseline data collection), adjusted for site and baseline scores as fixed effects. Since the Tampa site has a standardized, discharge planning process that involves Veteran education while the other sites have no discharge planning process, there may be different responses due to usual care between the Tampa versus other sites. Thus, we will first explore whether or not there is a differential treatment effect at the Tampa site by fitting a full model that allows for Tampa to have a differential time and group effect for each time point. Let  $y_{ij}$  be the depression score for person i at time j, then Full fixed effects model will be:

$$E(y_{ij}) = \beta_0 + \beta_1 Baseline_i + \beta_2 Tampa_i + \Sigma_s \beta_{3s} I(Site_i = s) + \beta_4 Time_{ij} + \beta_5 Group_i + \beta_6 Group_i *Time_{ij} + \beta_7 Tampa_i *Time_{ij} + \beta_8 Tampa_i *Group_i + \beta_9 Tampa_i *Group_i *Time_{ij}$$

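### The primary hypothesis covers 11 and 19 weeks, but only 11 weeks is tested as primary, and the test listed for 19 weeks does not estimate the 19-week effect

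*Combined protocol and SAP*

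**What the plan says.** The abstract gives the primary aim as "to test the effect of the intervention on stroke caregivers' depressive symptoms at approximately 11 and 19 weeks after baseline data collection". Section 5, Specific Aims and Hypotheses, words Hypothesis #1 (primary) as "Stroke caregivers who receive the intervention will have less depressive symptoms at approximately 11 and 19 weeks after baseline data collection". The Data Analysis section opens by restating that hypothesis: intervention caregivers "will have less depressive symptoms at approximately 11 and 19 weeks compared to stroke caregivers in the usual care group".

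That section then defines the endpoint with no visit attached: "Our primary endpoint is the caregiver depressive score". After setting out the mixed model it narrows the focus: "Of primary interest is the estimated within-site intervention effect at approximately 11 weeks after baseline data collection". In the reduced model this is the test of β5 = 0. The later visit is handled differently: "As a supplemental analysis we will assess long term intervention effects at the approximately 19 week after baseline data collection time point". The test given for it is β6 = 0 in the reduced model. In the full model it is β6 = 0 for the other sites and β6 + β9 = 0 for Tampa. The coding is "time (*Time*=0 for 11 weeks, 1 for 19 weeks".

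Every test uses the 0.05 level ("All tests will be performed at the" that level). The sample size rationale gives a 3.5-point effect, SD 8.2, 84 per group and 80% power, and names no visit.

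**The concern.** The hypothesis as worded joins two visits with 'and'. The analysis attaches the primary test to one of them and ranks the other below it. If the data show a benefit at 11 weeks and none at 19, the analysis text supports a claim of success, while the hypothesis text is only half met. Nothing in the plan says which statement governs. The choice could then be made after the results are known, and the headline conclusion would depend on it.

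The second difficulty is in the model. If the 19-week part of the hypothesis is to be assessed at all, even as a supplement, the listed contrast must measure the group difference at 19 weeks. It needs checking whether β6 does that.

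**Working it through.** **1. The plan's own figure.** The inputs come from the sample size rationale: difference 3.5, SD 8.2, 84 per group, 5% level. Sidedness is not stated, and two-sided is assumed.

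- Standard error of the difference: 8.2 × √(2/84) = 1.265.
- Expected z: 3.5 / 1.265 = 2.766.
- Power: Φ(2.766 − 1.960) = Φ(0.806) = 79.0%. The noncentral t gives 78.5%. Both are close to the stated 80%.
- Dropout: 84 / (1 − 0.30) = 120 per group, as planned.

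The stated power is therefore that of one comparison at one time.

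**2. How often the two statements of success part company.** Assume the same 3.5-point effect at both visits. Treat the 11-week and 19-week group differences as two z statistics, each with mean 2.766, and correlation r. The documents give no r, so a range is shown.

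- P(both significant) = Φ₂(0.806, 0.806; r), where Φ₂ is the bivariate normal distribution function.
- P(significant at 11 weeks, not at 19) = 0.790 − P(both significant).

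| r (assumed) | Both significant | 11 weeks only |
|---|---|---|
| 0.5 | 67.3% | 11.7% |
| 0.6 | 68.6% | 10.4% |
| 0.7 | 70.0% | 9.0% |
| 0.8 | 71.7% | 7.3% |

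Over r from 0.3 to 0.9 the ranges widen to 65% to 74% and 14% to 5%. If the 19-week effect were half as large (a further assumption), the 11-weeks-only outcome would occur in 54% to 51% of trials over that same wider range of r.

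**3. What β6 measures.** In the reduced model, with Time = 0 at 11 weeks and 1 at 19 weeks, the intervention-minus-control difference is:

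- at 11 weeks: β5
- at 19 weeks: β5 + β6
- change from 11 to 19 weeks: β6

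In the full model the difference at 11 weeks is β5 for the other sites and β5 + β8 for Tampa. At 19 weeks it is β5 + β6 for the other sites and β5 + β6 + β8 + β9 for Tampa. The plan's 19-week tests, β6 and β6 + β9, are the changes between visits in those two groups of sites.

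If the benefit is 3.5 points at 11 weeks and fully sustained, β6 = 3.5 − 3.5 = 0 in absolute terms, and the listed test rejects only at its 5% error rate.

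**4. The two listed tests taken together.** If the two visit-specific differences have equal variance and correlation r, the β5 and β6 statistics have correlation −√((1 − r)/2). This is −0.50 at r = 0.5 and −0.32 at r = 0.8. With a sustained 3.5-point effect, both listed tests reject in about 3% to 4% of trials. The 67% to 72% in step 2 therefore belongs to tests of the group difference at each visit, not to the pair that the plan lists.

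**The case against.** The strongest reply is that the primary test can be identified. The Data Analysis section says repeatedly that the 11-week effect is the one of primary interest, names its coefficient and calls 19 weeks supplemental. That is a ranking, although no formal testing order is given. The phrase naming both visits recurs in Aims 1, 2 and 3 and matches the assessment schedule, so it may only describe when outcomes are measured. The abstract's sentence labelled as the primary hypothesis names no visit; only the aim before it does. All of this stands. It means that the plan does contain a usable primary test.

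It does not remove the mismatch. The section that picks 11 weeks opens by stating the primary hypothesis at both visits, and no text says that one governs the other.

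A reader might also infer that a significant result at either visit would confirm the hypothesis, so that the error rate exceeds 5%. Two tests of the visit-specific differences would give 9.1% down to 7.8% for r from 0.5 to 0.8. The documents do not support this reading: nowhere do they say that either visit suffices, and the analysis ranks 11 weeks first.

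The power figures are approximate. They use an unadjusted two-sample formula, whereas the planned model adjusts for baseline, and they rest on a correlation that the documents do not give.

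**Conclusion.** The inconsistency is real but narrower than it may look. The plan has an identifiable 11-week primary test. What it lacks is a hypothesis that matches that test, so a significant 11-week result would count as success in the analysis without establishing the hypothesis as written.

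The gap of 7% to 12% of trials, and the 67% to 72% joint power against 79%, hold under four conditions: the hypothesis needs both visits, the effect is 3.5 points at both, SD is 8.2 with 84 per arm, and the correlation lies between 0.5 and 0.8. If 11 weeks alone is primary, the single-comparison power statement applies and there is no loss.

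The contrast error needs no such assumption. It follows from the stated time coding that no listed test evaluates the 19-week part of the hypothesis.

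**What to change.** - In the abstract, Section 5, the sample size rationale and the opening of the Data Analysis section, name the CES-D score at approximately 11 weeks after baseline as the single primary endpoint. This follows the priority that the analysis already gives.
- Keep 19 weeks as a supplemental analysis, and state that it cannot confirm the primary hypothesis on its own.
- In the Data Analysis section, test the 19-week effect as β5 + β6 = 0 in the reduced model. In the full model use β5 + β6 = 0 for the other sites and β5 + β6 + β8 + β9 = 0 for Tampa. If the change between visits is also of interest, β6 can stay, described as such.

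Promoting 19 weeks to a confirmatory secondary endpoint behind a gate would go beyond what the plan now says and is not needed here. The change does not touch the branch in which a Tampa difference leads to two site-specific primary tests; that needs its own rule.

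The cost is wording and one contrast, with no new data or participants. The downside is that a benefit seen only at 19 weeks could be reported only as exploratory.

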Rationale for Study Sample Size: The sample will consist of 240 caregivers. Assuming a standard deviation of 8.2, 84 subjects per group would achieve 80% power to detect a mean intervention effect size of 3.5 on depression at a 5% significance level. The sample size of 120 per group (i.e., intervention group, usual care group) was selected to account for the occurrence of a (30%) dropout rate. The 30% drop-out rate is a conservative estimate of attrition and is based on previous caregiver problem-solving intervention studies in the literature and on the attrition rates found in the internet intervention studies of our consultants, Drs. [name] and [name]. The expected effect size and variability was deemed reasonable based on a number of sources. In a study of caregivers of Alzheimer's patients, the investigative team described large changes pre- and post-treatment in a clinical setting, with depression from time of admission to 4 weeks post decreasing 20 points for "recovered" patients and 12 points for "still ill" patients. In a study of a telephone intervention to family caregivers of stroke caregivers, found an estimated 1 month treatment effect of 3.1.

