## **Randomization:**

The proposed study will use a two-group randomized design with 3 assessment points (baseline, approximately 11 weeks, and approximately 19 weeks). Following baseline assessments, the participant will be randomly assigned to one of the two study groups (Intervention or Usual Care). The Pocock-Simon covariate adaptive randomization procedure will be used so that there will be approximately equal number of subjects assigned to the two groups within each covariate level (depressed or not and high or low ADL) and within each study site. The statistician will develop the randomization scheme and share it with the project coordinator and a research staff member at each site. When a caregiver is enrolled in the study, this staff member at site will obtain the group assignment for that caregiver from the randomization system.

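### The primary model names a random person effect but no residual variance structure; as usually fitted it assumes equal spread at 11 and 19 weeks, which can misstate the standard error of the 11-week test

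*Combined protocol and SAP*

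**What the plan says.** In Data Analysis, Hypothesis #1, "the general linear mixed model for repeated measures will be used to model the follow-up depression times", with site and baseline score as fixed effects. Time is coded 0 at 11 weeks and 1 at 19 weeks. In the reduced model the primary test is therefore beta5 = 0, the group effect at 11 weeks. In the full model the corresponding tests are beta5 for the other sites and beta5 + beta8 for Tampa. The 19-week assessment is supplemental.

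The one statement on covariance is that correlation within a person is dealt with through "inclusion of a random person effect into the mixed model analysis". The model equations give expected values only. The plan does not mention a residual structure, variances by visit, an unstructured matrix, robust standard errors or a degrees-of-freedom method.

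The continuous secondary outcomes under Hypothesis #2 and the Barthel Index under Hypothesis #3 take over the same plan. The healthcare utilization counts use separate models and are not affected.

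**The concern.** A random person effect combined with one residual variance gives compound symmetry: a common variance at both visits and a single covariance. If the true variances differ, the model estimates something close to their average and uses it at each visit. The primary hypothesis is tested at one visit, so averaging does not cancel the error there. If week 11 is the more variable visit, the confidence interval is too narrow and the false-positive rate exceeds 5%. If week 11 is the less variable visit, the interval is too wide and power is lost.

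The wording also leaves a choice open. Two analysts could both follow the plan, one with a common residual variance and one with visit-specific variances, and report different p values for the primary test.

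**Working it through.** **Inputs.** From Rationale for Study Sample Size:
- "Assuming a standard deviation of 8.2"
- "mean intervention effect size of 3.5 on depression"
- "84 subjects per group would achieve 80% power"
- "at a 5% significance level" (sidedness is not stated; two-sided assumed)
- enrolment of 120 per group "to account for the occurrence of a (30%) dropout rate"

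From Randomization: two equal groups, since the procedure aims for an "approximately equal number of subjects assigned to the two groups".

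Assumed, because the documents give no figure: the ratio r = SD19/SD11, varied from 0.8 to 1.2, and a within-person correlation of 0.6 (simulation only). The value 8.2 is taken as the 11-week SD that enters the group comparison.

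**The plan's own figure.** SE = 8.2 × sqrt(2/84) = 1.265. Power = Phi(3.5/1.265 − 1.96) = 79.0% (78.5% with the noncentral t), close to the stated 80%. Exactly 80% needs 86.2, so 87, per group. A one-sided test would need 68, which does not match. Dropout: 84/0.7 = 120. The stated design is reproduced to within about one to two points of power.

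**Standard error of beta5, complete data.**
- Correct: sqrt(2 × SD11² / n).
- Random intercept with one residual variance: sqrt(2 × [(SD11² + SD19²)/2] / n).
- Ratio of the two: k = sqrt((1 + r²)/2).
- Actual type I error: 2 × [1 − Phi(1.96 × k)].
- Power: Phi(3.5/1.265 − 1.96 × k).

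The type I error depends on r alone; 8.2 and 84 cancel. Power uses both.

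| r | k | Model SE (correct 1.265) | Type I error | Power at 3.5 |
|---|---|---|---|---|
| 0.8 | sqrt(0.82) = 0.906 | 1.146 | 7.6% | 83.9% |
| 0.9 | sqrt(0.905) = 0.951 | 1.204 | 6.2% | 81.6% |
| 1.0 | 1.000 | 1.265 | 5.0% | 79.0% |
| 1.1 | sqrt(1.105) = 1.051 | 1.330 | 3.9% | 76.0% |
| 1.2 | sqrt(1.22) = 1.105 | 1.398 | 3.0% | 72.6% |

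The higher power at r below 1 is not a gain; it comes from a test that rejects too often.

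**Simulation check.** REML fits, 2,000 trials per setting, 84 per group, correlation 0.6, no loss or 15% random loss at week 19:
- r = 0.8, common variance, no loss: mean model SE 1.146 against an empirical SD of 1.277; type I error 7.8% (8.0% with loss).
- r = 1.2, common variance, no loss: 1.400 against 1.259; type I error 2.85% (2.5% with loss).
- Unstructured covariance, all settings: type I error 4.45% to 5.65%. The Monte Carlo standard error near 5% is sqrt(0.05 × 0.95/2000), about 0.5 points.
- r = 1.0: the two models agree (5.6% against 5.65% with no loss; 4.45% against 4.6% with loss).

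The empirical SD of the beta5 estimate was practically the same under both models, so the error lies in the reported standard error and not in the estimate.

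**Group-by-time term.** The variance of a within-person change is SD11² + SD19² − 2 × covariance. Using the average variance twice gives the same sum, so with complete data the beta6 test is not affected in this way.

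**The case against.** The strongest objection is that the plan never imposes equal variances. A reader might infer that it uses nothing but a random intercept and forces the two visits to share a variance. The text does not go that far. Equal variance comes from a common residual variance, and the plan neither states nor excludes one. A random person effect with visit-specific residual variances fits the wording. With two visits it is a full covariance, provided that the correlation is positive and the covariance does not exceed the smaller variance. This objection stands: the defect is an unstated residual structure whose usual default assumes equal variances.

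A reader might also infer that the primary test has an inflated false-positive rate. The documents do not support that either. They give one SD and nothing by visit, and the same 0–60 scale is administered by telephone at both follow-ups, about 8 weeks apart. The bounded scale does not help the stronger claim, because a floor or skewness present at both visits need not make their variances differ. The direction is unknown as well, and a larger 19-week spread would make the test conservative.

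Finally, the effect is modest for small differences. With SDs within 10% of each other the standard error is off by about 5%. This also stands, and it limits the priority of the point. It does not remove the case for a change that loses essentially nothing when the variances are equal.

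**Conclusion.** The point holds as a low-priority specification gap. If the random person effect is fitted with one common residual variance, the 11-week standard error is built from the average of the two visit variances and is correct only if these are equal. Over assumed SD ratios of 0.9 to 1.1 the type I error runs from about 6.2% down to 3.9%; over 0.8 to 1.2, from about 7.6% down to 3.0%. At a ratio of 1.2 power is about 73% instead of 79%. These figures rest on the assumed ratios, a two-sided 5% test and complete data; the power figures also use an 11-week SD of 8.2 and 84 per group. The simulations with 15% random loss at week 19 support the same pattern. Whether the visits differ in spread cannot be judged from the documents.

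**What to change.** In Data Analysis, replace the sentence on the random person effect with a full specification: an unstructured 2x2 within-person covariance for the 11- and 19-week scores. A random person effect with visit-specific residual variances is equivalent under the positive-correlation condition given above. Apply the same structure to the primary outcome, the continuous Hypothesis #2 outcomes and the Barthel Index.

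State a small-sample degrees-of-freedom method at the same time, for example Kenward-Roger. No defect in the degrees of freedom was shown, so the particular choice matters less than stating one in advance.

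The cost is one sentence in the plan and one extra variance parameter (three instead of two). No change in sample size or data collection is needed.
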